6.2 Medical history and concomitant diseases

The number and percentage of subjects with a medical history condition, including both previous and ongoing conditions will be summarized overall and by primary MedDRA system organ class (SOC) and preferred term (PT). In addition, this summary will also be done by seizure category.

All medical history data will be listed.

6.3 History of epilepsy

6.3.1 Epileptic seizure profile

The number and percentage of subjects experiencing each seizure category at any time prior to study entry will be summarized based on the ILAE Seizure Classification History eCRF.

The overall number and percentage of subjects with a history of Type I (POS), Type II (PGS), or Type III (Unclassified) seizures will also be summarized. A subject will be classified as having a history of Type I seizures if the subject has a history of Type IA, IB, or IC seizures. A subject will be classified as having a history of Type II seizures if the subject has a history of Type IIA1, IIA2, IIB, IIC, IID, IIE, or IIF seizures.

6.3.2 Classification of epileptic syndrome

The number and percentage of subjects with each epileptic syndrome will be summarized based on the Classification of Epileptic Syndromes eCRF and will include the number and percentage of subjects within each of the categories (localization-related, generalized, epilepsies and syndromes undetermined whether focal or generalized, and special syndromes) and subcategories of epileptic syndromes. Additionally, this summary will be done separately for each seizure category.

6.3.3 History of epileptic seizures

History of epileptic seizures, including the number and percentage of subjects with a history of status epilepticus, and quantitative summaries of epilepsy duration, age at diagnosis, and percent of life with epilepsy will be summarized separately for subjects with POS categorization at Baseline and for subjects with PGS categorization at Baseline.

For derivation of epilepsy duration and percent of life with epilepsy, see Section [3.10.2](#).

6.3.4 Historical seizure count

The Historical Seizure Count eCRF records the number of seizures of each type experienced by the subject during the 3 weeks prior to study entry. These data will be provided in a subject data listing.

6.4 Previous and concomitant medications

A listing of all medications (previous and concomitant) taken during the study will be presented. See Section 3.10.4.1 for the definition of previous, concomitant and follow-up medications.

For the summarization, similar AEDs are grouped and summarized together. For example: Valproate includes valproate sodium, valproate semisodium, valproate bismuth, valproate magnesium, valpromide, ergenyl chrono, valproic acid; Phenytoin includes phenytoin sodium, phenytoin calcium, mephenytoin, zentronal, metetoin, ethotoin, albutoin, hydantoin, phelantin, hydantol D, anirrit, dintoinal, fosphenytoin sodium, phenytoin, fosphenytoin, hydantoin derivatives, hydantoin; Phenobarbital includes phenobarbital sodium, methylphenobarbital, metharbital, alepsal, phenobarbital, kaneuron, epanal. Benzodiazepine AEDs that can be grouped by Bromazepam, Alprazolam, Cloxazolam, Diazepam group, Chlordiazepoxide, Clonazepam, Clobazam, Lorazepam, Clotiazepam, Temazepam, and Clorazepate are considered the same AED at the group level. Combination AEDs are not considered for grouping.

6.4.1 Non-AEDs taken at study entry

Identification of medications as a non-AED will be done using the UCB file:

AEDs_ATCs_SEP2017_FINAL_benzo_groups_23JUL2019.xls, which reflects AED evaluation result of concomitant Benzodiazepine from the data review meetings. Queries should be raised for any cases where this disagrees from the value entered in the eCRF field 'Core AED'.

The number and percentage of subjects in the SS taking non-AED medications at the time of study entry will be summarized by WHO-DRL anatomical main group, therapeutic group and preferred drug name.

6.4.2 Number of previous AEDs

The number of AEDs taken prior to study entry will be summarized based on the following categorization: 0-1 AEDs, 2-4 AEDs, and ≥ 5 AEDs. Identification of medications as an AED will be done using the UCB file:

AEDs_ATCs_SEP2017_FINAL_benzo_groups_23JUL2019.xls, which reflects AED evaluation result of concomitant Benzodiazepine from the data review meetings. This summary will only include AEDs which stopped prior to study entry. In addition, this summary will also be done by seizure category.

6.4.3 History of previous AED use

The number and percentage of subjects who had taken at least 1 AED prior to study entry will be summarized by preferred drug name. Identification of medications as an AED will be done using the UCB file: AEDs_ATCs_SEP2017_FINAL_benzo_groups_23JUL2019.xls, which reflects AED evaluation result of concomitant Benzodiazepine from the data review meetings. This summary will only include AEDs which stopped prior to study entry. Furthermore, the above described summary will be repeated by seizure category.

6.4.4 History of previous AEDs by reason for AED discontinuation

The number and percentage of subjects who had taken at least 1 AED prior to study entry and who had discontinued AED will be summarized overall, by reason for discontinuation of previous AEDs (insufficient efficacy, remission, adverse drug reaction, tachyphylaxis, unknown, other) and by age group in one table. Additionally, this summary will be done by seizure category.

Percentages for each reason for discontinuation will be relative to the number of subjects taking each AED.

6.4.5 VNS use and Number of AEDs taken at study entry

Identification of medications as an AED will be done using the UCB file:

AEDs_ATCs_SEP2017_FINAL_benzo_groups_23JUL2019.xls, which reflects AED evaluation result of concomitant Benzodiazepine from the data review meetings. The number and percentage of subjects taking 1, 2, and 3 AEDs at the time of study entry overall and separately by vagal nerve stimulation (VNS) use at study entry (no VNS or VNS not active versus currently active VNS) will be summarized. This analysis will be done by seizure category in addition.

6.4.6 AEDs taken at study entry

The number and percentage of subjects who had taken at least 1 AED at the time of study entry by WHO-DRL preferred drug name will be summarized. In addition, this analysis will be done by seizure category. Vagal nerve stimulation is allowed and will be counted as a concomitant AED.

6.4.7 Concomitant AEDs

The number and percentage of subjects taking concomitant AEDs overall and by WHO-DRL preferred drug name will be summarized by age group. In addition, this analysis will be done by seizure category.

6.4.8 Concomitant Non-AEDs

The number and percentage of subjects taking concomitant Non-AEDs overall and by WHO-DRL anatomical main group, therapeutic group and preferred drug name will be summarized overall by age group. In addition, this analysis will be done by seizure category.

7 MEASUREMENTS OF TREATMENT COMPLIANCE

BRV compliance will not be assessed due to the complexities associated with the calculation and interpretation of BRV compliance for this study.

BRV dosing will be provided in subject listings.

8 SAFETY ANALYSES

All presentation for safety parameters will be based on the SS and will be summarized by age group and seizure category as categorized in Section 4.8, and overall.

8.1 Extent of exposure

The Evaluation Period BRV exposure duration (in months) will be calculated as the date of the final dose of BRV during the Evaluation Period minus the date of the first dose of BRV in the Evaluation Period plus 1 day divided by 30. The overall study BRV exposure duration (in

months) including Up-Titration Period (only DE subjects), Evaluation Period and Down-Titration Period (only discontinued subjects) will be calculated as the date of the final dose of BRV in this study minus the date of the first dose of BRV in this study plus 1 day divided by 30.

Subject years of exposure are calculated as overall study BRV exposure duration (in months) multiplied by 30 divided by 360.

Both, the evaluation Period BRV exposure duration and the overall study BRV exposure duration will be summarized with quantitative descriptive statistics. The number and percentage of subjects with the following categories of Evaluation Period BRV exposure durations will also be presented: \leq 6 months, $>$ 6 to \leq 12 months, $>$ 12 to \leq 18 months, $>$ 18 to \leq 24 months, $>$ 24 to \leq 30 months, $>$ 30 to \leq 36 months, and $>$ 36 months.

The number and percentage of subjects exposed overall and by 6 month exposure durations (\leq 6 months of exposure, $>$ 6 months of exposure, $>$ 12 months of exposure, $>$ 18 months of exposure ...) will be presented overall and by modal dose category (see Section 3.2.8).

Additionally, the table will show mean subject years of exposure overall and by modal dose categories.

All BRV exposure data will be listed.

8.2 AEs

8.2.1 Overview of TEAEs

The overview of TEAEs will provide numbers and percentages of subjects with any TEAE, with any serious TEAE, with any TEAE that led to permanent discontinuation of BRV, with any drug-related TEAE, with any severe TEAE and with any drug-related serious TEAE. The number and percentage of subjects who died will also be summarized. This summary will be provided by age group in the SS. Additionally, it will be presented by core study, geographical region and seizure category as well as by modal dose category.

TEAEs which occurred during Up-Titration Period for DE subjects will be presented separately.

The criteria for classification of an AE as serious AE can be found in the protocol section 9.1.1.2. AEs are drug-related, if this is marked accordingly in the eCRF.

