3.2.3.1 Assignment of safety variables to study periods

In general, safety variables (e.g. AEs) will be allocated to the treatment group based on the dose most recently received. Safety outcomes which can be classified into more than 1 study period as per Section 3.2.3, based on partial dates of onset, will be classified into a study period based on the following prioritization: Up-Titration, Evaluation, Down-Titration, Safety, (for example, an AE that can be classified in both the Evaluation and Safety Period based on a partial date of onset due to a missing day entry, will be classified into the Evaluation Period).

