3.2.8 Modal dose calculation

Modal daily doses will be calculated across all study days on or after the day of first dose of BRV and up to and including the day of last dose of BRV. Modal daily dose is the most frequently taken daily dose during this period. In the event of a tie, the modal dose will be set to the lower of the tied doses. Modal daily dose will be categorized as follows:

Table 3–4: Dose group definitions for calculation of modal dose

Dose group label (mg/kg/day)
>=0.0 to <1.0
1.0 to < 2.0
2.0 to < 3.0
3.0 to < 4.0
>=4.0

For each subject, the mode will then be calculated and they will be assigned to one of the groups in [Table 3-4](#) overall, and by 6-month cohort.

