- Incidence of TEAEs leading to permanent discontinuation of BRV

A subject number table will be provided that identifies subjects with any TEAE after the first dose of BRV. This table will be presented by intensity, relationship, treatment-emergence overall and by every subcategory of these variables.

The overview of TEAE, the incidence of TEAEs and incidence of serious TEAEs will be presented by age group, by seizure category, by dose group and by core study.

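### Dose-based TEAE tables group subjects by a whole-study modal dose that counts days after the event, and the SAP does not reconcile this with its own rule of allocating AEs by the most recent dose

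*SAP*

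**What the plan says.** Four places in the SAP bear on this.

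- **3.2.3.1** sets a general rule: "safety variables (e.g. AEs) will be allocated to the treatment group based on the dose most recently received". It stands in a section on assigning safety outcomes to study periods. The SAP defines no dose-based treatment groups; Section 3.6, whose title refers to them, holds only the titration schedule for directly enrolled subjects.
- **3.2.8** defines the modal dose: "Modal daily doses will be calculated across all study days on or after the day of first dose of BRV", through to the last dose. Whichever dose was taken on the most days is the mode, and equal counts are resolved downward: "In the event of a tie, the modal dose will be set to the lower of the tied doses". Each subject is then placed in a Table 3-4 band "overall, and by 6-month cohort".
- **8.2.1** presents the TEAE overview by several subgroups: "Additionally, it will be presented by core study, geographical region and seizure category as well as by modal dose category".
- **8.2.2** says the overview, the incidence of TEAEs and the incidence of serious TEAEs "will be presented by age group, by seizure category, by dose group and by core study". It does not say whether the dose group is modal or at onset. The only dose groups in the SAP are those of Table 3-4, whose title ties them to the modal dose.

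Section 2 allows BRV dose changes at any time on clinical judgment, apart from the guided Up-Titration Period.

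**The concern.** TEAEs and serious TEAEs are the primary variables, and the tables in 8.2.1 and 8.2.2 are the only AE tables planned by dose. Two things are wrong with how they are fixed.

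First, a programmer cannot tell from the text which rule governs the 8.2.2 tables. The definition of dose group points to modal dose, while 3.2.3.1 points to the most recent dose. The overview is promised in both sections, once by modal dose category and once by dose group, with no statement that these are the same.

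Second, under the modal reading the grouping is partly set after the event and can be changed by it. An AE that prompts a lasting reduction helps to decide the column in which its subject is counted. A reader is likely to take a table of TEAEs by dose as information on a dose relation, and this construction can weaken that relation or, in an extreme case, reverse it.

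**Working it through.** The SAP states no figure to reproduce, because all summaries are descriptive. The check has two parts.

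**1. When does an AE change column?** The 3.2.8 rule was applied to assumed dose histories over 3 × 360 = 1080 days. The doses and timings are illustrations only.

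| History | By dose at onset | By modal dose |
|---|---|---|
| AE at 4, reduced to 2 mg/kg/day after day 30, 90, 180, 360 or 540 | ≥4.0 | 2.0 to <3.0 |
| Same, reduced after day 541, 720 or 900 | ≥4.0 | ≥4.0 |
| AE at 4, 60 days on 4, 20 days on 2, then stopped | ≥4.0 | ≥4.0 |
| AE at 4.9, reduced to 4.0 after 90 days | ≥4.0 | ≥4.0 |
| AE at 2, then 900 of 1080 days on 4 | 2.0 to <3.0 | ≥4.0 |

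At day 540 the two doses tie at 540 days each, and the tie rule sends the subject down. So a downward move needs a reduction that crosses a Table 3-4 boundary and is taken for at least as many days as the higher dose. A lasting increase moves an earlier AE up.

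**2. How large could the effect be?** Assumptions, none of them from the SAP except that 3 years echoes its minimum treatment duration:

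- half the subjects start on a high dose and half on a low dose, in different bands;
- all are followed for T = 3 years;
- AEs occur at constant rates h = 0.40 per year on the high dose and l = 0.20 on the low dose;
- a fraction p of high-dose AEs leads to permanent reduction to the low dose.

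A high starter becomes modal-low if the reduction comes by T/2 = 1.5 years. Reductions occur at rate hp, so:

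- share of high starters moved: q = 1 − exp(−hpT/2) = 1 − exp(−0.6p)
- P(AE, modal-high column) = 1 − exp(−hT)/exp(−hpT/2) = 1 − exp(−1.2 + 0.6p)
- P(AE, modal-low column) = [(1 − exp(−lT)) + q]/(1 + q) = (0.451 + q)/(1 + q), because every moved subject has had at least one AE

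For p = 0.5: q = 1 − exp(−0.3) = 0.259; high = 1 − exp(−0.9) = 0.593; low = (0.451 + 0.259)/1.259 = 0.564.

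| p | q | Modal-high, % with AE | Modal-low, % with AE | High-dose AEs counted under low (simulated) |
|---|---|---|---|---|
| 0 | 0 | 70 | 45 | 0% |
| 0.1 | 0.058 | 68 | 48 | 7% |
| 0.2 | 0.113 | 66 | 51 | 13% |
| 0.5 | 0.259 | 59 | 56 | 33% |
| 0.8 | 0.381 | 51 | 60 | 52% |

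Simulation of the same model agrees to within about a point; one run gave 60% against 57% at p = 0.5. Event rates by dose at onset return about 0.40 and 0.20 per year at every p.

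Dividing by the subject-years that 8.1 gives by modal dose does not repair this. At p = 0.5, simulated events per subject-year by modal dose are 0.29 and 0.27, because the events and the time sit in the same wrong column.

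**The case against.** The other side has several good points.

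- **The two rules need not conflict.** A reader might infer that 8.2.1 contradicts 3.2.3.1. The documents do not go that far: the rule is stated as a general one, concerns assignment to study periods, and refers to a treatment group that is never defined. A specific table instruction can stand beside a general default. What remains is that the SAP never says which applies where.
- **The 8.2.2 tables may not be modal.** A reader might infer that every dose view is modal. Section 8.2.2 does not say so, and 3.2.3.1 could support the other reading. That is an ambiguity, although Table 3-4 as the sole definition makes modal dose the likelier reading.
- **The shift is conditional.** Late reductions, within-band reductions and prompt discontinuation move nothing.
- **Large effects need large p.** TEAEs include all events after first dose whatever their cause, so reduction after half or more of them is an extreme assumption. At 10% most of the gradient survives. Even with no misplacement a twofold rate ratio shows as 70% against 45%, about 1.55-fold, so not all of the flattening comes from modal dose.
- **Up-Titration is partly handled.** Section 8.2.1 shows those TEAEs separately and 8.2.2 tabulates by study period, so low-dose titration events are not the main problem.
- **No dose-response aim is stated**, and individualized dosing confounds dose-at-onset rates as well.

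These points narrow the finding but leave two defects standing: an undefined grouping for primary-variable tables, and a modal grouping that the event can alter.

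**Conclusion.** The point holds in a limited form. The TEAE overview is grouped by a whole-study modal dose that counts days after the event; the dose grouping in 8.2.2 is unclear; and neither is reconciled with 3.2.3.1. Misplacement can go down or up and depends on the dose history.

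The size cannot be known from the SAP, which gives no frequency of dose reduction. Under the stated assumptions the gap between columns falls from 25 points with no reductions to 20 at 10%, about 15 at 20% and 3 at 50%, and reverses only at the extreme of 80%. It would be wrong to conclude that the planned tables will hide or reverse a dose relation; they can weaken one to an unknown degree. The overall, age-group and seizure-category TEAE tables are unaffected. The change should be made, but the main safety summary does not depend on it.

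**What to change.** 1. In 8.2.2, define dose group. For each dose-based AE table in 8.2.1 and 8.2.2, state whether modal dose or dose at onset governs, and align 3.2.3.1 with that choice.
2. Add a summary of TEAEs and serious TEAEs by the Table 3-4 category of the daily mg/kg dose at AE onset. Give events per 100 subject-years at that dose, with time summed from the dosing records.
3. If the modal-dose AE table is kept, label it as a subject-level subgroup that is not evidence of a dose relation. Removing it is not necessary.

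The cost is SAP wording, one derived dose-at-onset variable with subject-time by dose, and one extra table. Dosing data are already recorded and listed. The downside is that dose-at-onset rates remain descriptive, because dosing is individualized, and the table should say so.

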8.2.2 Incidences of TEAEs

Incidence summaries will be presented by SOC and PT. These tables will include the number and percentage of subjects and number of events by SOC and PT. For the number of subjects by PT, if a subject experiences multiple AE within the same PT, then that PT will only be counted once. As with the PT, for the number of subjects by SOC, if a subject experiences multiple AEs within the same SOC, then that SOC will be counted only once. Percentages will be calculated out of the number of subjects at risk in the SS unless otherwise stated.

Incidence tables are sorted alphabetically by SOC and decreasing by frequency in PT in the overall column. In case of ties, PTs are sorted alphabetically.

The following TEAE summaries will be presented:

- Incidence of TEAEs

- Incidence of TEAEs by 3-month time interval (one table presenting TEAEs starting within time intervals and one presenting those ongoing in the time interval)
- Incidence of drug-related TEAEs by 3-month time interval
- Incidence of TEAEs by 1-year time interval
- Incidence of TEAEs by total duration of exposure cohort (as per categories defined in Section 3.2.7)
- Incidence of TEAEs by study period (Up-Titration, Evaluation, Down-Titration, Safety)
- Incidence of TEAEs by maximum intensity
- Incidence of drug-related TEAEs
- Incidence of serious TEAEs
- Incidence of drug-related serious TEAEs
- Incidence of TEAEs for TEAEs occurring in at least 5% of subjects
- Incidence of TEAEs by 3-month time intervals for TEAEs occurring in at least 5% of subjects
- Incidence of TEAEs by 3-month time intervals for TEAEs occurring in at least 5% of subjects by geographical region
- Incidence of non-serious TEAEs occurring in at least 5% of subjects
- Incidence of non-serious TEAEs occurring in at least 5% of subjects by geographical region
- Incidence of drug-related TEAEs occurring in at least 5% of subjects
- Incidence of drug-related TEAEs occurring in at least 5% of subjects by geographical region
- Incidence of TEAEs leading to permanent discontinuation of BRV
- Incidence of drug-related TEAEs leading to permanent discontinuation of BRV

Tables presenting incidence of TEAEs occurring in at least 5% of subjects will include only TEAEs occurring on or above the reporting threshold of 5% in any age group or geographical region.

Additionally, following incidence tables will be presented by total duration of exposure categories:

- Incidence of serious TEAEs
- Incidence of TEAEs leading to permanent discontinuation of BRV

A subject number table will be provided that identifies subjects with any TEAE after the first dose of BRV. This table will be presented by intensity, relationship, treatment-emergence overall and by every subcategory of these variables.

The overview of TEAE, the incidence of TEAEs and incidence of serious TEAEs will be presented by age group, by seizure category, by dose group and by core study.

8.2.3 Incidences of TEAEs of interest

Incidence of TEAEs of interest as per Section 9.1.1.3 in study protocol will be presented separately, by age group as well as by age group and 3-month time interval.

AEs of interest will be identified based on MedDRA search criteria, which are documented outside of the SAP. All AEs which are listed in “BRV List of TEAE Topics of Interest Final 24 Aug 2018.xlsx” document (provided from UCB) and are flagged with “P” or “B” in appropriate column are AEs of interest for this study.

8.3 Clinical laboratory evaluations

Clinical laboratory results will be summarized using conventional units. Observed values and change from Baseline values for hematology, biochemistry (including hepatic monitoring of ALT, AST, ALP, total bilirubin, and GGT) and endocrinology parameters will be summarized for Baseline, each scheduled visit in the Evaluation Period, Last Value on Treatment, and the Safety Visit (if available). These summaries will be repeated separately for data collected during the Up-Titration visits for DE subjects.

Presentation of urinalysis results will consider subjects by age group for whom sample collection is feasible due to the constraints on collection for subjects below 4 years of age in the protocol. Following age groups will be presented: ≥ 4 to < 12 years, ≥ 12 years to < 17 years and overall.

In microscopic urinalysis, a small sample of urine is centrifuged to remove the liquid. The sediment is then examined under a microscope. In the urinalysis laboratory test group, other than qualitative responses, a listing of microscopic analysis parameters will be provided; no summaries of microscopic analysis findings are planned.

Response categories are negative, 1+, 2+, and 3+ for the quantitative urinalysis parameters occult blood, leukocytes, glucose, protein, and ketones and negative and positive for nitrates. Outcome values for these parameters are mapped to the levels Negative, 1+, 2+, and 3+ as follows for purposes of summary tables and the determination of PCST:

Table 8-1: Urinalysis categorization

Category	Definition
Negative	“Negative”, “NEGATIVE” or other outcomes that clearly reflect a negative finding
1+	“1+”, “+”, “Trace”, “TRACE” or other outcomes that clearly reflect trace amount
2+	“2+” or “++”
3+	“3+”, “+++” or other outcomes that clearly reflect the data above 3+ (eg, “4+”, “5+” etc.) or more than 4 plus signs (eg, “++++”, “+++++” etc.)

For qualitative urinalysis parameters (occult blood, leukocytes, glucose, protein, ketones, and nitrates), the number and percentage of subjects with each response category will be summarized for Baseline, EV, each scheduled visit during the Evaluation Period for which urinalysis parameters were scheduled to be assessed, Last Value on Treatment, and the Safety Visit. Percentages for each parameter will be relative to the number of subjects with a microscopic urinalysis assessment at each time point. The summary will be repeated for the Up-Titration period for DE subjects.

The number and percentage of subjects with any post-Baseline PCST value, any PCST low value, and any PCST high value for hematology, biochemistry and urinalysis will be summarized for the Evaluation and Safety Periods separately and for the Evaluation and Safety Period combined by laboratory parameter overall and by age group. PCST criteria for hematology and biochemistry are presented in Appendix Section 12.1 A urinalysis value is considered PCST abnormal if an upward shift of at least 2 degrees from the Baseline occurs under investigational treatment. Percentages will be relative to the number of subjects with an on-treatment assessment.

Observed values and change from Baseline value tables will only present scheduled visits, whereas for PCST tables, values reported at an UV will be summarized under the preceding scheduled visit if the abnormality was not already reported at the preceding scheduled visit. Treatment emergent for this analysis includes any PCST laboratory abnormalities observed during the Evaluation Period.

A subject number table will be provided that identifies subjects with a PCST finding after the first dose of BRV for each type of laboratory abnormality.

All laboratory parameters (planned and unplanned parameters and assessed on scheduled and unscheduled visits) will be provided in subject data listings.

